5. DEFINITIONS

5.1 Clinical concern about bleeding

The main objective of this prognostic study is to estimate how well test results from the post-operative blood samples predict CCB, i.e. bleeding that is likely to cause direct patient harm or indirect patient harm by precipitating a non-routine pro-haemostatic treatment or re-operation for bleeding for which no direct surgical cause is identified.

A participant will be classified as having experienced the primary outcome of CCB if any of the three circumstances below is documented within the designated time interval:

- i. Post-operative blood loss (volume collected through chest drain) greater than 600mL at T5¹ (interval 2a).
- ii. Intervention with a non-routine early pro-haemostatic treatment (EPT) defined as additional protamine after initial heparin reversal during interval 2b², fresh frozen plasma (FFP), cryoprecipitate, platelets, anti-fibrinolytic drug, recombinant human coagulation factors VII [rFVII] or fibrinogen concentrate during interval 2b (T3-T6 ; Figure 1).

¹ Chest drain volume after 6 hours from admission to CICU is likely to be an unreliable marker of actual bleeding because of contamination with tissue fluid. There is no universally effective threshold for clinical concern about post-operative bleeding even at T5, so 600 ml total during this interval is a pragmatic clinical suggestion. Chest drain volumes at T6 will continue to be collected but it is very difficult to suggest a plausible 'threshold' value at this time point that will reflect 'actual bleeding'.

² Medical notes and details for those patients who only received additional doses of protamine and no other non-RBC products will be reviewed. Those with only one dose of protamine, administered after the post-operative sample is collected but prior to admission to CICU will be considered "routine" administration of protamine. The medical notes for all other instances will be reviewed and the protamine will be classified as "routine" or "therapeutic" as appropriate. Those considered to have received "routine" dose(s) of protamine will not be included in the definition of EPT.

STATISTICAL ANALYSIS PLAN

COPTIC: Coagulation and platelet laboratory testing in cardiac surgery
A prognostic study of associations between post-operative test results and subsequent bleeding

- iii. Reoperation for bleeding recorded during hospital stay and failure to demonstrate a surgical cause for bleeding³.

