2.2 Overview of COPTIC study design

COPTIC is a prospective observational study of patients undergoing cardiac surgery at the Bristol Heart Institute.

- i. All participants undergo standard pre-operative, anaesthetic, surgical and post-operative care according to existing protocols.
- ii. Blood samples are obtained in the operating theatre at the following time-points:

STATISTICAL ANALYSIS PLAN

[figure not shown]
COPTIC: Coagulation and platelet laboratory testing in cardiac surgery
A prognostic study of associations between post-operative test results and subsequent bleeding

- a. Immediately before induction of anaesthesia (*pre-operative sample; 9.5mls*)
- b. Immediately after reversal of heparin anticoagulation (*post-operative sample; 18.5mls*)

Data are collected until 12 hours after admission to Cardiac intensive care unit (CICU). The study timings are shown in Figure 1.

Figure 1: Timeline for COPTIC study

T0: time of pre-op sample

T1: cessation of CPB

T2: administration of final routine dose of protamine

T3: time of post-op sample

T4: time of arrival in CICU

T5: 6 hours after arrival in CICU

T6: 12 hours after arrival in CICU

T7: CICU discharge

Interval 1 time interval between pre-op and post-op samples [T3-T0]

Interval 2a post-op sample to 6 hours after admission to CICU [T5-T3]

Interval 2b post-op sample to 12 hours after admission to CICU [T6-T3]

Interval 2 time interval between post-op sample and CICU discharge [T7-T3]

This SAP refers to the analysis of post-operative Multiplate test results, ROTEM test results and TEG test results (part of Study B). A separate analysis plan will be written for the analyses of the other laboratory results from post-operative samples (also Study B).

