2.6.1 Primary laboratory predictors (test results considered likely to predict CCB)

Test result	Laboratory test and platform	Likely predictor of CCB
Platelet count	FBC (XE-2100 cell counter)	LOW test result
Multiplate ADP test AUC	Multiplate	LOW test result
Multiplate AA test AUC	Multiplate	LOW test result
Multiplate TRAP test AUC	Multiplate	LOW test result
Multiplate ADR test AUC	Multiplate	LOW test result
ROTEM intem CT	ROTEM	HIGH test result
ROTEM intem alpha	ROTEM	LOW test result
ROTEM intem mcf	ROTEM	LOW test result
ROTEM intem ml	ROTEM	HIGH test result
ROTEM intem maxV	ROTEM	LOW test result
ROTEM intem maxV-t	ROTEM	HIGH test result
ROTEM extem CT	ROTEM	HIGH test result
ROTEM extem alpha	ROTEM	LOW test result
ROTEM extem mcf	ROTEM	LOW test result

STATISTICAL ANALYSIS PLAN

COPTIC: Coagulation and platelet laboratory testing in cardiac surgery
A prognostic study of associations between post-operative test results and subsequent bleeding

ROTEM extem ml	ROTEM	HIGH test result
ROTEM extem a10	ROTEM	LOW test result
ROTEM extem maxV	ROTEM	LOW test result
ROTEM extem maxV-t	ROTEM	HIGH test result
ROTEM fibtem mcf	ROTEM	LOW test result
ROTEM fibtem a10	ROTEM	LOW test result
ROTEM extem mcf - fibtem mcf	ROTEM	LOW test result
ROTEM intem CT - heptem CT	ROTEM	HIGH test result
TEG CK rmin	TEG	HIGH test result
TEG CK angledeg	TEG	LOW test result
TEG CK ma	TEG	LOW test result
TEG CK ly60	TEG	HIGH test result
TEG CK rmin – CKH rmin	TEG	HIGH test result

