3.5 Protocol deviations

The protocol states that all post-operative samples should be collected after the return of cell saver and/or pump blood, and after all "routine" protamine doses have been administered. All samples that are recorded as not being collected at this specific time will be reviewed and excluded if necessary. The overlap with the return of pump blood is of particular concern.

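### Section 5.1, footnote 2 calls a lone protamine dose after the post-operative sample routine by rule, which conflicts with the plan's own timeline, sampling rule and outcome definition

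*SAP*

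**What the plan says.** SAP section 2.2 (Figure 1) sets the order of events: "T2: administration of final routine dose of protamine", then "T3: time of post-op sample". Section 3.5 repeats the requirement that samples follow the return of cell saver or pump blood and every routine protamine dose. For departures it says: "All samples that are recorded as not being collected at this specific time will be reviewed and excluded if necessary".

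Section 5.1(ii) includes in EPT "additional protamine after initial heparin reversal during interval 2b", and interval 2b runs from T3 to T6. Footnote 2 then qualifies this. It opens by saying that the notes of "those patients who only received additional doses of protamine and no other non-RBC products will be reviewed". It continues: "Those with only one dose of protamine, administered after the post-operative sample is collected but prior to admission to CICU will be considered" routine. Only the remaining instances are classified as routine or therapeutic from the notes. Doses labelled routine do not count as EPT.

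The derivation table in section 6.1 gives the window for therapeutic protamine as interval 1 or interval 2b. Sections 5.1(ii) and 6.2 give interval 2b only.

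Section 2.6.1 lists "ROTEM intem CT - heptem CT" and the corresponding TEG difference (CK rmin minus CKH rmin) as primary predictors, with a high result expected to predict CCB. Intem CT and TEG CK rmin are primary predictors in their own right.

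**The concern.** On the plan's own timeline, no routine dose can follow a correctly timed sample. A dose after T3 is therefore either not routine, which makes it EPT, or routine, which makes the sample early. Footnote 2 lets the dose be routine for the outcome and does not refer to section 3.5, so the same patient's sample can still be analysed as correctly timed.

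The results most at risk are the two paired differences, intem CT and CK rmin. I take the paired differences to isolate residual heparin, as the pairing implies; the SAP does not say so. Protamine given soon after sampling is the treatment most closely tied to that signal. These variables enter Models 2D (ROTEM) and 2E (TEG), and Step 2 of section 7.2 uses those models to choose the best platform.

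**Working it through.** The SAP states no figure that depends on this rule, so there is none to reproduce. The check is a comparison of passages, followed by an illustration on assumed inputs.

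**1. Passages side by side, for one dose after T3 and before CICU with no other non-red-cell product**

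| Status of the dose | Sample, under Figure 1 and 3.5 | EPT, under 5.1(ii) |
|---|---|---|
| Routine | Taken before T2: timing deviation | No |
| Therapeutic | Correctly timed | Yes, hence CCB |
| Footnote 2 as written | Not linked to 3.5 | No |

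The first two rows are each consistent. The third agrees with the first only if the sample is also treated as a deviation, and nothing in footnote 2 requires that.

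**2. Protamine window.** Interval 1 is T0 to T3, so section 6.1 admits therapeutic protamine given before the sample, while 5.1(ii) and 6.2 do not. Section 7.2 distinguishes any CCB from post-operative CCB, which may explain the wider window, but 6.1 does not tie the window to either outcome.

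**3. Possible effect on discrimination.** Assume a test with unit SD and mean 0 in patients without CCB, 0.3 in patients with CCB by another route, and d in lone-dose patients without another CCB criterion. Then

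AUC = Σ w(case) w(control) Φ[(m(case) − m(control))/√2] / [Σ w(case) × Σ w(control)].

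Example with other CCB 20%, lone-dose group 5%, remainder 75%, d = 1.0:
- Coded non-CCB: [0.75 × Φ(0.212) + 0.05 × Φ(−0.495)] / 0.80 = (0.75 × 0.584 + 0.05 × 0.310) / 0.80 = 0.567.
- Coded CCB: [0.20 × 0.584 + 0.05 × Φ(0.707)] / 0.25 = (0.20 × 0.584 + 0.05 × 0.760) / 0.25 = 0.619.
- Difference: 0.619 − 0.567 = 0.052.

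I varied other CCB (20% or 35%), the group size (1% to 10%, which is 24 to 240 of the planned 2400) and d (0 to 1.5). The AUC with the group coded CCB minus the AUC with it coded non-CCB gave:

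| Other CCB 20% | d = 0 | d = 0.5 | d = 1.0 | d = 1.5 |
|---|---|---|---|---|
| Group 1% | −0.004 | +0.004 | +0.012 | +0.018 |
| Group 5% | −0.017 | +0.020 | +0.052 | +0.078 |
| Group 10% | −0.028 | +0.036 | +0.093 | +0.139 |

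With other CCB at 35%, the differences lie inside this range (−0.019 to +0.120).

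**4. Why any exclusion must ignore outcome.** Assume other CCB in 30% of test-positive and 25% of test-negative patients, with a lone dose in 40% and 3% of them, independent of other CCB.
- Group kept as non-CCB unless another criterion is met: OR = (0.30/0.70) / (0.25/0.75) = 1.29.
- Only the otherwise non-CCB lone-dose patients removed: [0.30/(0.70 × 0.60)] / [0.25/(0.75 × 0.97)] = 0.714/0.344 = 2.1.
- All lone-dose patients removed: the factors 0.60 and 0.97 cancel within each row, and the OR is 1.29 again.

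The rise to 2.1 comes from selecting on outcome.

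**The case against.** Figure 1 shows the intended order, and section 3.5 expects departures from it. A dose called routine that follows the sample fits the description in 3.5, so such samples may already go to review and be excluded. The amendment log says this provision was added for samples taken before routine protamine. Footnote 2 can also be read as a deliberate exception to 5.1(ii), keeping ordinary protamine out of an EPT component whose limitations sections 7.4.6 and 7.4.7 already address.

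Much of this stands. It cannot be said that these patients remain in the analysis with unreviewed samples. But exclusion under 3.5 is discretionary, no criterion is given, the stated particular concern is pump blood, and footnote 2 does not trigger the review. An exception to 5.1(ii) also holds only if the dose is routine, and then the sample is early.

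A reader might infer that these patients are coded the wrong way. The SAP does not show this. If the doses were routine, the outcome code is right and only the sample timing is at fault. Nor are the patients automatically non-CCB: drain loss above 600 mL at T5 or a qualifying reoperation still makes them CCB. A reader might also infer bias toward no association, but table 3 shows that the sign depends on whether the group carries residual heparin effect.

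The sensitivity analyses do not settle the matter. In the second analysis of 7.4.6, patients with EPT alone are recoded as free from CCB, so the protamine label cannot alter their outcome there. Neither 7.4.6 nor 7.4.7 varies the protamine rule or addresses sample timing.

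**Conclusion.** The inconsistency is real and can be read directly from the text. For patients with a lone dose between the sample and CICU admission and no other non-red-cell product, the outcome code and the sample timing cannot both follow the plan's rules. Section 6.1 adds a separate conflict over the protamine window.

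The consequence is not established. The SAP gives neither the size of the group nor its test results. In the illustration, if the group carries residual heparin effect (a shift of 0.5 SD or more), the present rule gives a lower AUC than coding the group as CCB. With no shift, the order reverses. If the group is 1% of patients, the difference is at most 0.018 either way. These figures rest wholly on assumed inputs and show only that the question is worth checking. The point warrants a clarification and a sensitivity analysis; it does not show that the heparin-effect results are wrong.

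**What to change.** Reconcile footnote 2, Figure 1, section 3.5, section 5.1(ii) and section 6.1 so that no dose is routine for the outcome while the sample before it is treated as correctly timed. In particular:

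- Apply the notes-based routine or therapeutic classification to the lone-dose group, as footnote 2 already does for all other instances.
- Automatically flag any sample followed by a dose judged routine as a section 3.5 timing deviation.
- State one protamine window for each outcome, consistently in 5.1, 6.1 and 6.2.
- Report how many patients are in the group.
- Repeat Models 2D and 2E with the group coded as CCB, coded as non-CCB, and excluded regardless of outcome.

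The cost is SAP wording, notes review for one further group, some model reruns and possibly the loss of a few samples. Which doses are clinically routine is for the sponsor to decide.

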5.2 Secondary endpoint definitions

- i. Red cell transfusion expressed as: (i) any vs. none; (ii) total number of units transfused;(iii) >4 units vs. ≤4 units⁴ occurring intra-operatively or during CICU stay (interval 2).
- ii. Non-routine pro-haemostatic treatments (see [section 5.1](#) for definition), occurring in interval 2, and expressed as: (i) any vs. none and (ii) total number of units or dose administered.
- iii. Serious post-operative complications, i.e. death, myocardial infarction (MI), any stroke, acute kidney injury (AKI) and sepsis during hospital admission.

Secondary endpoints i) and ii) will be extracted from INNOVIAN and will cover the period of CICU admission, with information on therapeutic protamine for the time interval 2b extracted from the CRFs (time from the post-operative sample to 12 hours post-CICU admission). Secondary endpoints detailed in iii) will be extracted from the PATS Database or INNOVIAN. Due to known limitations in the completeness of the PATS database for some of these data, INNOVIAN data will also be utilised to identify these outcomes; firstly by the event being recorded in INNOVIAN and secondly by an electronic review of the following five free text fields extracted from INNOVIAN:

- Intensivists Review
- Problems (Physician Daily Review and Plan)
- Progress note (Physician Daily Review and Plan)
- Surgical Review
- CICU Ward round
- Plan of care on discharge

The search terms to be used are as follows:

	Innovian search terms	Context terms
Death	n/a (all captured in PATS/NHS Strategic Tracing Service [NSTS])	
Myocardial Infarction	Myocardial infarction Infarct	Q wave MI/myocardial infarction Non-Q wave MI/myocardial infarction

³ In order to account for reoperations which were conducted due to surgical cause of bleeding, relevant electronic notes for all patients who required a reoperation will be reviewed by a cardiac surgeon (GJM). Any patient identification details will be masked. Those who, in the opinion of the surgeon, had a surgical cause of bleeding will be excluded from the definition of CCB.

⁴ RBC transfusion of 1-2 units may occur at any time during or after surgery, usually in response to low haematocrit for which bleeding is only one cause. Thus, the number of red cell units transfused reflects poorly the extent of bleeding. However, larger volume RBC transfusions (arbitrarily defined as >4 units) more reliably reflect clinically important bleeding.

STATISTICAL ANALYSIS PLAN

COPTIC: Coagulation and platelet laboratory testing in cardiac surgery
A prognostic study of associations between post-operative test results
and subsequent bleeding

	MI STEMI NSTEMI ST elevation	Low cardiac output Cardiogenic shock IABP
Any stroke	Stroke Transient ischaemic attack, Hemiplegia Paralysis Paraplegia Dysphasia Cerebral/central nervous system (CNS) infarct/embolus	Loss of sensation CNS deficit Focal neurology Motor loss/deficit Sensation loss/deficit Brainstem Seizure Fit
Acute renal injury	Haemofiltration Haemodialysis Haemodiafiltration Dialysis Filtration Acute renal failure AKI Renal injury Kidney injury	New haemofiltration/dialysis CVVH RRT Already on dialysis
Sepsis	Chest infection Wound infection Mediastinitis Graft site infection Sternal wound infection Urinary tract infection Septic Sepsis Blood borne infection	Dehiscence Deep sternal wound Oozy sternum Positive blood culture Positive wound culture SIRS

Each of these secondary outcomes will be recorded as having occurred if there is evidence of a positive event within PATS or within INNOVIAN, including the review of free text.

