4. COPTIC DATA COLLECTION

4.1 Data sources

Information will be collected from the following sources:

Data sources and identification details for linkage

Data type	Brief description	Identification for linkage
CRF Data	Information on time samples were taken, time of CICU admission, blood loss 6 and 12 hours post CICU admission, red blood cells (RBC) and non-RBC transfusions during operation and post-	STUDYID (identifies patient), COPTIC SAMPLEID (identifies sample), operation date, Hospital number/BRI Trust number

STATISTICAL ANALYSIS PLAN

COPTIC: Coagulation and platelet laboratory testing in cardiac surgery
A prognostic study of associations between post-operative test results
and subsequent bleeding

Data type	Brief description	Identification for linkage
	operatively up to CICU admission.	
Clinical data	Data extract from PATS Database including reoperation details (Section 5.1 (iii) and clinical outcomes as detailed in Section 2.5 (c).	Hospital number/BRI Trust number, name, sex, date of birth, operation date
Clinical data	Data extract from INNOVIAN, clinical information system of hourly data for time spent in CICU. These data include red blood cells (RBC) and non-RBC transfusions during CICU admission and clinical outcomes as detailed in Section 2.5 (c).	Hospital number/BRI Trust number, operation date
Clinical data	Creatinine test results for all consenting COPTIC patients, restricted to the closest test prior to the operation (pre-op) and any tests after the operation but within 7 days of the operation date (post-op)	BRI Trust number, date of birth
Laboratory test results	Results from all laboratory tests detailed in Section 2.5.1. These are transferred from the coagulation lab as a single file (FBC) or in the form of many separate files of weekly results (Multiplate, TEG and ROTEM).	All post-operative samples are identified by the COPTIC SAMPLEID (as in CRF data). The date of test will also be used to aid linkage.

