6.2 Secondary endpoints

New variable	Rules	Data sources
RBC transfusion	Any RBC transfusion during interval 2	INNOVIAN clinical information

⁵ Diagnosis, evaluation, and management of acute kidney injury: a KDIGO summary (Part 1). Kellum *et al.* Critical Care 2013, 17:204

STATISTICAL ANALYSIS PLAN

COPTIC: Coagulation and platelet laboratory testing in cardiac surgery
A prognostic study of associations between post-operative test results and subsequent bleeding

New variable	Rules	Data sources
(binary)	(the time between post-operative samples are taken and discharge from CICU).	system
RBC >4 units (binary)	Any RBC transfusion >4 units during interval 2 (the time between post-operative samples are taken and discharge from CICU).	INNOVIAN clinical information system
Non-routine pro-haemostatic treatments (binary)	Any platelet, FFP, cryoprecipitate or rFVII transfusion during intervals 1 and 2 (the time between post-operative samples are taken and discharge from CICU), or therapeutic protamine during interval 2b (the time between post-operative samples are taken and 12 hours post CICU-admission).	INNOVIAN clinical information system and CRFs
Serious post-operative complications:		
Death (binary)	Vital status (alive vs. died in theatre OR died in hospital).	PATS Database (updated with NSTS data)
MI (binary)	Any MI occurring before discharge OR death from MI in hospital.	PATS Database, INNOVIAN clinical information system and death certificate data
Stroke (binary)	Any peri- OR post-operative neurological complication (stroke; transient ischaemic attack; hemiplegia; paralysis; paraplegia; dysphasia; cerebral/CNS infarct/embolus).	PATS Database, INNOVIAN clinical information system
AKI (binary)	Serum creatinine increased by ≥ 26.5 $\mu\text{mol/l}$ from the pre-operative value within 48 hours of surgery OR serum creatinine increased ≥ 1.5 times the pre-operative value within 7 days of surgery.	Creatinine data
Infection during hospital admission (binary)	Any infective complication (chest infection; wound infection; mediastinitis; graft site infection; sternal wound infection; urinary tract infection; septic; sepsis; blood borne infection).	PATS Database and INNOVIAN clinical information system

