6.4 Other variables

More can be entered here

STATISTICAL ANALYSIS PLAN

COPTIC: Coagulation and platelet laboratory testing in cardiac surgery
A prognostic study of associations between post-operative test results and subsequent bleeding

New variable	Rules
Age	(Operation date – DOB)/365.25
BMI	Weight (kg) / Height (cm) ² * 10,000
Time in theatre	Cumulative bypass time; cumulative cross-clamp time
Cardiac procedure	CABG, Valve, other (or combination)
Pre-operative kidney function	Pre-operative serum creatinine and dialysis information will be used to calculate estimated glomerular filtration rate (eGFR): Cockcroft-Gault formula: $eC_{Cr} = \frac{(140 - \text{Age}) \times \text{Mass (in kilograms)} \times [0.85 \text{ if Female}]}{72 \times \text{Serum Creatinine (in mg/dL)}}$ Or, when serum creatinine is measured in $\mu\text{mol/L}$: $eC_{Cr} = \frac{(140 - \text{Age}) \times \text{Mass (in kilograms)} \times \text{Constant}}{\text{Serum Creatinine (in } \mu\text{mol/L)}}$ where Constant is 1.23 for men and 1.04 for women.
Blood products as units	Divide volume (ml) by 280 to obtain red cells units Divide volume (ml) by 225 to obtain platelet units Divide volume (ml) by 260 to obtain FFP units Divide volume (ml) by 175 to obtain cryoprecipitate units Selected as averages of given NHSBT product specifications NB: Calculation of total units will be defined as missing if the total doses=0 and any of intra-op, grey area, INNOVIAN data are missing. i.e. they will not be recorded as missing if any doses given at any of these times is recorded, even if data at least one other time are missing.
Operative priority	This will be defined as “elective” or “urgent”. Any few emergency or salvage procedures will be classified as urgent.
Cardiac procedure	This will be classified in four groups; CABG only; CABG+valve; Valve alone; other
Involvement in other studies	An indicator will be created for each trial as follows: 
 (Y/N) for participation in HARVeST, PROMPT, VERDICT, Protection1 (n/liberal group/restrictive group) for TITRe2 (n/intervention group/control group) for PASPORT There will be no indicator for concurrent involvement in smaller trials.

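### The SAP gives incompatible windows, sources and agent lists for the red cell and pro-haemostatic secondary endpoints, so the same patient can be coded differently by section

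*SAP*

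**What the plan says.** **Window.** Section 2.2 defines "Interval 2 time interval between post-op sample and CICU discharge [T7-T3"]. Section 5.2 counts red cells "occurring intra-operatively or during CICU stay (interval 2") and counts pro-haemostatic treatment in interval 2. In 6.2 the larger-volume red cell row reads "Any RBC transfusion >4 units during interval 2 (the time between post-operative samples are taken and discharge from CICU"), and the row for any red cells uses the same window.

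**Source.** Section 5.2 says "Secondary endpoints i) and ii) will be extracted from INNOVIAN and will cover the period of CICU admission", with the CRFs brought in for therapeutic protamine. Section 4.1 describes INNOVIAN as "hourly data for time spent in CICU", and says the CRFs hold red cell and other transfusions in theatre and up to CICU arrival. In 6.2 both red cell rows name INNOVIAN alone, while the pro-haemostatic row names INNOVIAN and the CRFs. Section 5.3 says the data exist only for the CICU stay. The missing-data rule for unit totals in 6.4 refers to "any of intra-op, grey area, INNOVIAN data are missing".

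**Agents.** Section 5.2 takes its pro-haemostatic list from 5.1, which includes "anti-fibrinolytic drug, recombinant human coagulation factors VII [rFVII] or fibrinogen concentrate during interval 2b". The 6.2 rule begins "Any platelet, FFP, cryoprecipitate or rFVII transfusion during", gives intervals 1 and 2 as the window, and then explains this in brackets as the time from the post-operative sample to CICU discharge. It adds therapeutic protamine in interval 2b. Section 4.2 says the Haematology department supplies data on anti-fibrinolytics, rFVII and fibrinogen concentrate.

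**The concern.** These endpoints feed the logistic models and ROC analyses that relate post-operative tests to the secondary outcomes (analysis A4 and section 7.4.3). If the window in a definition is wider than the source used to fill it, events in the uncovered part are recorded as absent. Here the uncovered part is T3 to T4, the period immediately after the sample that supplies the predictors. Footnote 4 presents more than 4 units as the version that better reflects important bleeding, and a version that depends on a count is easily pushed below its cut by missing units.

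The agent list raises a second problem. Dropping fibrinogen concentrate removes a treatment from an analysis whose primary predictors include the FIBTEM measures. The reference to interval 1 raises a third: a test taken at T3 cannot predict treatment given before T3. Two programmers working from this SAP could produce different endpoint variables, each with a section to support it.

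**Working it through.** The SAP states no figure that can be reproduced on this point, so the check is a comparison of sections followed by an illustration.

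**1. Red cells: window against source.** The window is T3 to T7 (2.2, 5.2, 6.2). The source in 5.2 and in both 6.2 rows is INNOVIAN, which covers T4 to T7 (4.1). The gap is T3 to T4. The CRFs cover it according to 4.1, and 6.4 implies that theatre and intermediate data enter unit totals. Section 5.3 says the data do not exist outside CICU, which conflicts with 4.1 and 6.4. Section 6.2 has no row for unit totals, so the binary and total versions could end up with different windows.

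**2. Pro-haemostatic treatment: list and source.** The list in 5.1, used by 5.2, is protamine, FFP, cryoprecipitate, platelets, anti-fibrinolytic drug, rFVII and fibrinogen concentrate. The list in 6.2 is platelets, FFP, cryoprecipitate, rFVII and therapeutic protamine. Two agents are lost, and the 6.2 row does not name the Haematology data. On source, 5.2 limits the CRFs to protamine and 6.2 does not.

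**3. Pro-haemostatic treatment: window.** Interval 1 is T0 to T3 (2.2), so it ends where the bracketed description in 6.2 begins. The rule contradicts both its own bracket and 5.2.

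**4. Coding of hypothetical patients.**

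| Patient | 5.2 window and list | 5.2 source sentence | 6.2 rule and source |
|---|---|---|---|
| A: 5 red cell units in T3–T4, none in CICU | any; >4 | none; ≤4 | none; ≤4 |
| B: 3 units in T3–T4, 2 in CICU | 3 + 2 = 5, so >4 | 2, so ≤4 | 2, so ≤4 |
| C: platelets only, in T3–T4 | treated | untreated | treated |
| D: fibrinogen concentrate only, in interval 2b | treated | unclear | untreated |
| E: platelets only, before T3 | untreated | untreated | treated |

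Patient D is CCB-positive under 5.1. Patients A, B and D lose an event under 6.2, and patient E gains one.

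**5. Illustration of size (assumed inputs only).** Let p1 and p0 be the true risks with abnormal and normal tests, s1 and s0 the shares of true events captured, and assume no false events. Then

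OR_obs = [s1·p1/(1 − s1·p1)] / [s0·p0/(1 − s0·p0)].

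Take p1 = 0.40 and p0 = 0.20:

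- Full capture: (0.40/0.60)/(0.20/0.80) = 2.67.
- 10%, 20% or 30% missed in both groups: 2.56, 2.47 and 2.39. The last is (0.28/0.72)/(0.14/0.86).
- 30% missed with abnormal tests and 10% with normal: (0.28/0.72)/(0.18/0.82) = 1.77.

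Take p1 = 0.20 and p0 = 0.10:

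- Full capture: 2.25.
- Equal misses of 10%, 20% or 30%: 2.22, 2.19 and 2.16.
- Misses of 30% and 10%: 1.65.

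Equal under-capture matters little, while unequal under-capture matters a good deal. The illustration does not cover events added from interval 1.

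**The case against.** A reader might infer that treated patients are bound to be scored as untreated on both endpoints, and that the error always runs towards no event. The SAP does not support that reading, for four reasons.

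- The pro-haemostatic row in 6.2 names the CRFs, so for products given before CICU there is a conflict with 5.2 but no certain omission.
- Section 6.4 suggests that theatre and intermediate doses enter the unit totals. The loss follows only if the source cells of 6.2 are applied literally. For the any-versus-none versions it affects only patients with no other counted treatment.
- The interval 1 wording works in the opposite direction.
- Section 5.3 declares a CICU-only limit openly, as a departure from the protocol. This would be a full answer if 5.2 and 6.2 had been narrowed to match and if 4.1 and 6.4 did not point to data from before CICU. As it stands, it is one more conflicting statement.

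It can also be said that the theatre wording for red cells in 5.2 is harmless. The sample is taken in the operating theatre, so the phrase may mean only the theatre part of interval 2. That is a fair reading, and the phrase needs clarifying rather than deleting. Finally, nothing in the SAP shows that the missed patients are mainly early heavy bleeders, so unequal under-capture is an assumption.

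**Conclusion.** The point holds as an unreconciled set of definitions. Followed literally, 6.2 misses red cells given between the sample and CICU arrival, leaves out two agents that 5.2 counts, and admits pro-haemostatic treatment given before the sample. Misclassification can therefore go in either direction.

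Its size cannot be derived, because the SAP gives neither the number of patients treated only in T3–T4 or only with the omitted agents, nor the number treated only before T3. The odds ratios above show sensitivity under assumed risks and are not estimates for this study.

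The scope is secondary endpoints i and ii. This gap in sources and agents does not extend to the primary outcome, because 6.1 refers to the 5.1 list and names the CRFs and the Haematology department among its sources. The plan should be corrected before these endpoints are derived.

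**What to change.** Make 5.2, 5.3, 6.2 and 6.4 agree, and apply the same rules to the binary and unit-total versions:

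- **Window:** interval 2 (T3 to T7) for both endpoints, keeping the stated interval 2b limit for therapeutic protamine. Delete the reference to interval 1 in the pro-haemostatic row of 6.2. State in 5.2 that the theatre wording for red cells means only the time in theatre after T3.
- **Agents:** use the 5.1 list in 6.2, adding anti-fibrinolytic drugs and fibrinogen concentrate.
- **Sources:** CRFs for T3–T4, INNOVIAN for T4–T7, and the Haematology data for the agents that 4.2 says it covers. Name them in each row of 6.2 and in 5.2, and add a rule for unit totals.
- **Consistency:** correct the CICU-only statement in 5.3, and define the intermediate period that 6.4 mentions.

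The cost is SAP wording and a recode of data that the SAP describes as collected. One condition applies: the SAP does not say that CRF transfusions are split at T3 or that the Haematology records carry times. If they cannot be placed relative to T3, the SAP should say so and restate the endpoint window to match the data actually used.
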